Baseline Visit 2 (RAAS Characterization): After Baseline Visit 1, subjects will be placed on an isocaloric low sodium diet for 6 days prepared by the metabolic phenotyping core at the BWH Center for Clinical Investigation for assessment of RAAS activation. Subjects will be asked only to consume the prescribed diet, containing 10 ± 2 mEq Na⁺, 100 ± 2 mEq K⁺, and 1000 ± 50 mg Ca²⁺ per 24 hours.

- 1) 24 hr urine will begin on the morning of this visit for volume, Na, K, Cr, cortisol, and aldosterone excretion rate.
- 2) Urine pregnancy test for females as appropriate.
- 3) Urine Na and Cr (rescheduled if subject is not in sodium balance).
- 4) Interval history and physical, including orthostatics.
- 5) Subjects will begin fast and lie supine overnight.
- 6) Fasting blood for PRA, serum aldosterone, K. DNA collection for genetic testing is optional.
- 7) Resume ad lib diet and administer study medication (eplerenone vs. placebo) to be started on the following day.

Substudy Visit 1 (Optional): Subjects will present on a low carbohydrate diet, after an overnight 12 hr fast. We will obtain:

- 1) STAT serum pregnancy test for females as appropriate.
- 2) Cardiac ¹⁸F-FDG-PET/CT to assess arterial inflammation.

Randomization and Blinding: Subjects will be randomized 1:1 to receive eplerenone

**Mineralocorticoid Receptor Antagonism for Cardiovascular Health in HIV
The MIRACLE HIV Study**

50mg daily or identical placebo for 12 months. The randomization list, stratified by gender, statin use and presence of plaque will be generated by the biostatistician and kept by the research pharmacy. Daily dosing starts at 50 mg daily for the first week to avoid hypotension and will be increased to 50 mg twice daily at the 1 week safety visit. The study will be double-blinded. All subjects will receive lifestyle modification as described below.

Safety Visits (1 wk, 2 wk, 4 wk, 3 mo, 6 mo, 9 mo post baseline visits): Subjects will only present after an overnight 12 hr fast for the 6 month visit. All safety visits include:

- 1) Urine pregnancy test for females.
- 2) Interval history and physical, including vitals.
- 3) Blood for Cr, K. Blood for markers of heart disease and inflammation for the 6 month visit only.
- 4) Collection of used study drug and provision of new supply.

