The CCTA protocol is as follows, and is based on the standard clinical CCTA protocol at MGH: Prior to imaging, intravenous (IV) access will have been obtained in an arm or hand vein, usually in the right antecubital vein. The subject's blood pressure will be taken, and ECG leads will be attached to monitor heart rate and rhythm. Sublingual nitroglycerin (0.3-0.9 mg, typically 0.6 mg) or transdermal nitroglycerin (0.6-0.8 mg/hr for ~45 minutes) will also be administered as per standard protocol for cardiac CT scans. Contraindications to nitroglycerin include known narrow angle glaucoma, hypotension with systolic blood pressure < 90 mm Hg, known severe aortic stenosis, or use of phosphodiesterase type 5 inhibitor (e.g. sildenafil, tadalafil, vardenafil) within the 5 days prior to scan. A prospectively-ECG triggered noncontrast CT of the heart is obtained to measure coronary calcium. The test bolus method will be used to plan the CTA timing, via a test bolus injection of nonionic iodinated contrast medium (approximately 20 ml), followed by a flush of saline solution (approximately 40 ml). Contrast-enhanced CT

Mineralocorticoid Receptor Antagonism for Cardiovascular Health in HIV The MIRACLE HIV Study

acquisition will then take place. Based on subject size, 60-100 ml of nonionic iodinated contrast (iopamidol 370 g/cm³, Isovue 370, Bracco Diagnostics, Princeton, NJ) will be injected, followed by a flush of 40 ml of saline solution. After a delay based on the test bolus, a CT acquisition will be performed from the aortic arch to the diaphragm: tube voltage 70 - 120 kVp, tube current-time product reference 320 mAs, detector collimation 2 x 128 x 0.6 mm or 2 x 196 x 0.6 mm. A number of high-resolution images of the heart at slightly different time-positions within the cardiac cycle will be reconstructed, of which the best phase will be used to evaluate the coronary artery lumen, plaque distribution, and plaque morphology.

Cardiac Positron Emission Tomography (PET)

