CTA contrast medium: CTA requires the intravenous administration of iodinated contrast medium. These contrast media have been known to cause renal failure, particularly in subjects with a pre-existing renal impairment. Adequate hydration will also be emphasized to each study participant. The contrast dose in coronary CTA has decreased with the introduction of faster scanners. The dose required will be between 60 to 100 ml. Allergic reactions to iodinated contrast media may cause skin reactions or in very rare occasions result in breathing difficulty and hypotension. Subjects will be closely

Mineralocorticoid Receptor Antagonism for Cardiovascular Health in HIV The MIRACLE HIV Study

monitored for the development of any allergic reactions. To minimize risk from iodinated contrast, subjects with previous allergic reactions to iodine-containing contrast media or signs of renal failure or history of renal disease will be excluded from the CTA study. Additional safety criteria will be implemented by measuring serum creatinine and excluding subjects with serum creatinine >1.5 mg/ml or estimated GFR <60 mL/min/1.73m 2 . Metformin use is an exclusion criteria for the study, so the risk of lactic acidosis will be avoided.

Nitroglycerin: Nitroglycerin is commonly used in subjects with angina pectoris and is generally considered safe. The side effects and risks of nitroglycerin are generally mild and of short duration and include hypotension, tachyarrhythmia, headache, lightheadedness, and visual disturbance. Subjects who are on sildenafil, tadalafil, or vardenafil (PDE5 inhibitor) will need to stop these drugs at least 5 days prior to receiving nitroglycerin on the day of the coronary CTA scan. If baseline systolic blood pressure is below 90, nitroglycerin will not be given. If a participant's blood pressure were to drop precipitously or if the participant develops symptoms, standard clinical care will be provided. Other contraindications to nitroglycerin include severe aortic stenosis or hypertrophic obstructive cardiomyopathy.

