Eplerenone: The eplerenone dose of 50mg daily has been used safely in previous studies to improve coronary circulation in individuals with Type 2 diabetes and by others in numerous studies of patients with CVD. This dose is FDA approved for indefinite use in patients with hypertension or left-ventricular dysfunction following myocardial infarction. Hyperkalemia is a potential side effect of eplerenone use, and any subject with serum K > 5.5 mEq/L at screen will be excluded. During the study, a subject who has an elevated K of > 5.5 mEq/L at any study visit will have a recheck; if the K remains elevated after recheck, the dose will be decreased to 50mg daily. If the K remains elevated > 5.5 mEq/L, the subject will be excluded from the study. Additionally, subjects who experience symptoms of hyperkalemia and have a K > 5.0 mEq/L will be excluded from continued participation in the study. Subjects who have hypotension (SBP<90 mmHg) at any study visit after titration to full dose eplerenone 50mg twice daily will be given a dose reduction to 50 mg daily. If a subject remains hypotensive (SBP <90 mmHg) or symptomatic of hypotension at the reduced dose they will be dropped from the study. Since subjects with renal insufficiency may require reduced dosing based on creatinine clearance, subjects with serum creatinine > 1.5 mg/dl will also be excluded. Other rare side effects include dizziness, fatigue, and diarrhea; these will be assessed for throughout the study. The effect of eplerenone on an embryo, fetus, or on a breastfeeding infant, is unknown and may be harmful. Because of these unknown risks, women cannot take part in this study if they are: pregnant, trying to become pregnant, breastfeeding. If women become pregnant or think they are pregnant during the study, they must stop taking the study medication and will be withdrawn from the study. We have received FDA IND exemption for the use of eplerenone in HIV for insulin resistance and recently received an FDA IND exemption for application in CVD indices in HIV. Protease inhibitors with the most significant effect on CYP3A4 will be exclusionary as in our prior trials of HIV patients. We will also exclude subjects using other strong inhibitors of CYP3A4, as well as CYP3A4 inducers. Furthermore, all subjects will be carefully monitored for side effects, including frequent potassium and BP monitoring. A 50mg twice daily dose of eplerenone has been chosen, such that even if concentrations do increase somewhat through pharmacokinetic interactions, we expect the drug to be well tolerated. The dose of 100 mg/day has been effective in numerous studies of non-HIV patients and is expected to be effective in the proposed studies.

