Hyperkalemia is a potential side effect of eplerenone use, and contraindications for the use of eplerenone include serum K > 5.5 mEq/L at initiation. Therefore, any subject with serum K > 5.5 mEq/L at screen will be excluded from the study. During the study, a subject who has an elevated K of > 5.5 mEq/L at any study visit will have a recheck; if the K remains elevated after recheck they will be excluded from the study. Additionally, subjects who experience symptoms of hyperkalemia and have a K > 5.0 mEq/L will be excluded from continued participation. Subjects who have symptomatic hypotension at any study visit after titration to full dose eplerenone 50mg twice daily will be given a dose reduction to 50 mg daily. Since patients with renal insufficiency may require reduced dosing based on creatinine clearance, subjects with renal insufficiency (serum creatinine > 1.5 mg/dl) will also be excluded from participation. Other side effects have been reported and include dizziness, fatigue, diarrhea, headache, stomach pain, cough, breast enlargement or breast enlargement, rash, abnormal vaginal bleeding. Rare but serious side effects include chest pain, tingling in arms and legs, loss of muscle tone, weakness or heaviness in legs, confusion, lack of energy, cold, gray skin or irregular heartbeat. These potential side effects will be assessed for throughout the study. Exclusion criteria during the study include initiation of ACE-I, ARB, or spironolactone; Hgb < 10; ALT > 3.0x ULN; persistent hyperkalemia (K > 5.5 mEq/L despite recheck and/or symptoms of hyperkalemia if K > 5.0 mEq/L). If a subject remains hypotensive (SBP < 90 mmHg) or symptomatic of hypotension after a dose reduction of eplerenone to 50 mg for this same reason during the study, they will be dropped from the study.

Data Safety Monitoring Plan

Prior to the start of study, a data safety monitoring board will be created and this board will consist of a statistician, a clinician not directly related to the research project, but one who is familiar with HIV infection and its complications, and a member of the HIV community. This board will meet quarterly to review any potential side effects or adverse events in relation to the use of eplerenone or participation in the study. The

Mineralocorticoid Receptor Antagonism for Cardiovascular Health in HIV The MIRACLE HIV Study

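### Sections VII and IX give different triggers for the same mandatory dose reduction for low blood pressure, and they part for a full-dose subject with SBP below 90 mmHg and no symptoms

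*Combined protocol and SAP*

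**What the plan says.** Section VII (Risks and Discomforts), Eplerenone paragraph: "Subjects who have hypotension (SBP<90 mmHg) at any study visit after titration to full dose eplerenone 50mg twice daily will be given a dose reduction". The reduced dose is 50 mg daily. The next step is: "If a subject remains hypotensive (SBP <90 mmHg) or symptomatic of hypotension at the reduced dose they will be dropped from the study".

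Section IX (Monitoring and Quality Assurance): "Subjects who have symptomatic hypotension at any study visit after titration to full dose eplerenone 50mg twice daily will be given a dose reduction". The reduced dose is again 50 mg daily. Later in the same paragraph, a subject is to be dropped who "remains hypotensive (SBP < 90 mmHg) or symptomatic of hypotension after a dose reduction of eplerenone to 50 mg for this same reason".

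The only other text that ties this dose to blood pressure is the titration step at the 1 week visit, in Section V under Safety Visits. It makes the increase depend on tolerance, blood pressure and laboratory results. It gives no threshold and says nothing about later visits. No section says which of the two reduction rules governs.

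**The concern.** Both sentences are mandatory, apply from the same point in treatment and lead to the same dose. They differ only in who qualifies: Section VII needs a systolic reading below 90 mmHg, while Section IX needs symptoms. Staff who work from Section IX, which is where one would look for monitoring rules, have no stated instruction to reduce a subject with a low reading and no complaints. Section VII requires that reduction.

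The situation is foreseeable. The first week is given at 50 mg daily specifically to guard against hypotension. Subjects with blood pressure above 140/90 mmHg are excluded, and stable beta-blockers and most calcium channel blockers are allowed. Safety visits include "Interval history and physical, including vitals", so low readings without symptoms can be picked up and staff need one rule for them. Because the trial is double-blind, the rule also has to be applied uniformly without knowledge of the assignment.

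What is at stake is subject safety and consistent dosing.

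**Working it through.** No arithmetic applies beyond the daily dose (2 × 50 mg = 100 mg/day before the reduction, 50 mg/day after it). The check sets the two triggers side by side for a subject at full dose.

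| State at full dose | Section VII trigger | Section IX trigger |
|---|---|---|
| SBP below 90, symptoms | met | met |
| SBP below 90, no symptoms | met | not met |
| SBP 90 or above, symptoms | not met | depends on reading |
| SBP 90 or above, no symptoms | not met | not met |

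1. **First and last rows.** The sections agree.
2. **Second row.** This is the firm difference. Section VII requires the reduction. Section IX's trigger is not met, and Section IX states no other action for this subject.
3. **Third row.** The answer under Section IX depends on whether its term carries an implied pressure limit, and the text does not settle this. The point therefore does not rest on this row.
4. **What was intended.** Section IX's removal rule speaks of a subject who still has SBP below 90 or still has symptoms after a reduction made for that reason. That wording looks back to a reduction made for either criterion, yet the reduction sentence a few lines earlier carries only one. Section VII's removal rule also names both. A common trigger of SBP below 90 mmHg or symptomatic hypotension is thus the most natural reading of what was meant. This is an inference from the removal rules; the documents do not state it.
5. **Other text.** The week 1 titration step has no threshold, so it does not decide between the two.

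**The case against.** The strongest reply is that the rules are not mutually exclusive. Section IX does not say that a subject with SBP below 90 and no symptoms stays on the full dose, and Section VII does not say that a symptomatic subject does. A site that reduces on either trigger breaks neither rule. The potassium rules in the same two sections show what a true contradiction looks like: when potassium is still above 5.5 mEq/L on recheck, Section VII lowers the dose and Section IX removes the subject. All of this stands. It makes the hypotension point milder, but does not remove it, because neither section tells staff to combine the triggers and one who reads only Section IX will not see the pressure criterion.

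A reader might also infer that it is an error for either reduction trigger to differ from the removal rule. The documents do not support that. Removal is a second step for subjects already reduced, and it may properly be wider than the first step. For example, a subject reduced for SBP below 90 who recovers to 92 but still has symptoms can sensibly be dropped under Section VII. The removal rule matters here only as evidence of intent.

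Nor do the nitroglycerin precautions for the CT scan, which also use a systolic limit of 90, settle the question. They concern another drug and another purpose.

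Finally, safety visits include vitals and a physician is on call at all times. These limit the consequences without resolving which trigger applies.

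**Conclusion.** The point holds in a narrow form. The same mandatory reduction has two different triggers, and they differ firmly for one kind of subject: full dose, SBP below 90 mmHg, no symptoms. The conclusion rests on the plain wording of the two sentences and on the absence of any text giving one section precedence.

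It would go too far to say that the two sections cannot both be followed, or that Section IX keeps such a subject at 100 mg/day. It would also go too far to say that the plan calls for reduction on symptoms at any systolic pressure, since neither section states that threshold.

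The documents give no frequency of hypotension, so no number of affected subjects can be given. Power and alpha are not affected. The inconsistency should be fixed because it sits in a safety dosing rule and is cheap to remove.

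**What to change.** In both Section VII (Eplerenone) and Section IX, replace the reduction trigger with one sentence built from the protocol's own removal criterion: *SBP <90 mmHg or symptomatic of hypotension at any study visit after titration to 50 mg twice daily: reduce to 50 mg daily.* Leave the removal rule as it is. Do not add that symptoms count at any pressure. That would be a new clinical threshold, and since dizziness and fatigue are listed as side effects of eplerenone, it could turn non-specific complaints into dose reductions.

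The cost is one reworded sentence in each section, with no new visits, procedures or subjects. There is a small downside: a few more subjects may be reduced below the intended 100 mg/day than under either sentence alone. The activities listed for remote visits in the COVID-19 contingency plan do not name a blood pressure reading, so the pressure criterion can be applied there only if a reading is available. The rewording does not change that.

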- a) Worsening markers of inflammation and heart disease across the spectrum stratified by presence and absence of excess VAT and presence and absence of coronary plaque (i.e. increased worsening across the following groups: low VAT/absence of plaque, low VAT/presence of plaque, high VAT/absence of plaque, high VAT/presence of plaque).

III. Subject Selection

Inclusion/Exclusion:

Inclusion Criteria: Up to 160 HIV male and female subjects will be consented to achieve the number of evaluable subjects. 42 subjects will be consented for the optional study.

Subjects will be included for:

- 1) Ages 40-65 years
- 2) Antiretroviral use (ART) >12 months and viral load <100 copies/mL
- 3) VAT > 110cm²

Exclusion Criteria:

- 1) Antihypertensive use including, ACE Inhibitor, ARB, MR blockade, diuretic, potassium (K) supplementation; or BP > 140/90 mmHg. Stable use (>3 months) of beta-blockers or calcium channel blockers (CCB) (except verapamil) is allowed.
- 2) Unstable statin use <12 months. Stable use (>12 months) is allowed.
- 3) Use of full dose ritonavir, nelfinavir, clarithromycin, and other strong inhibitors of CYP3A4, as well as CYP3A4 inducers.
- 4) Continuous oral steroid use (equivalent to prednisone \geq 5 mg daily) within the last 3 months.

**MIneralocorticoid Receptor Antagonism for CardiovascuLar hEalth in HIV
The MIRACLE HIV Study**

- 5) Uncontrolled diabetes requiring insulin and/or HbA1c > 7.5%.
- 6) Creatinine (Cr) > 1.5 mg/dL or estimated GFR<60 mL/min/1.73m².
- 7) K > 5.5 mEq/L.
- 8) Hemoglobin < 10 g/dL.
- 9) Known liver disease or ALT >3x ULN.
- 10) History of congestive heart failure, stroke, myocardial infarction, or known coronary artery disease.
- 11) Pregnant, actively seeking pregnancy or breastfeeding. Women of childbearing age may be on a non-hormonal form of contraception.
- 12) Estrogen, progestin derivative, or other sex steroid use within last 3 months. Stable physiologic testosterone replacement (> 3 months) is acceptable.
- 13) Current bacterial or other infections.
- 14) Active substance abuse.
- 15) Significant radiation exposure over the course of the year prior to randomization (e.g., radiation therapy, PCI, catheter ablation of arrhythmia) within 12 months of randomization.
- 16) Previous reaction or contraindication to gadolinium.
- 17) Coronary artery luminal narrowing >70% on coronary CTA.

Source of subjects and recruitment methods:

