Upon confirmation of eligibility, subjects will be given the option through a formal consenting process to participate in the substudy prior to randomization. Participation in the main study will not be affected if subjects choose to decline participation in the substudy; however, subjects withdrawn from the main study will be withdrawn from the substudy.

If subjects do not qualify for the main study following completion of both screening visits, subjects will be given the option to participate in an optional blood sampling visit.

Treatment assignment and randomization:

During the Baseline Visit randomization will be done. Subjects will be randomized 1:1 to receive eplerenone PO 50mg daily or identical placebo for 12 months. The randomization list, stratified by gender, statin use, and presence of plaque will be generated by the biostatistician and kept by the research pharmacy. Daily dosing starts at 50 mg for the first week to avoid hypotension and will be increased to 50 mg twice daily at the 1 week safety visit. The study will be double-blinded. All subjects will receive lifestyle modification as described below.

Prior to randomization in all cases, the subject's primary care physician will be consulted regarding the appropriateness of the protocol including the lifestyle modification program with the subject's permission. Subjects are not eligible if they do not meet all of the enrollment criteria.

In the event that a subject wishes to withdraw from the study, the subject will be asked to return all unused study medication.

V. Study Procedures

Data Collection

Screening Visit 1 (to determine eligibility):

We will obtain:

- 1) Informed consent, history and physical, urine pregnancy test for females.
- 2) Blood for Cr, K, ALT, CBC, HbA1c, and HIV viral load.

Screening Visit 2 (to determine eligibility): Subjects will present after a 12 hr fast. If eligible from Screening Visit 1, we will obtain:

- 1) Urine pregnancy test for females as appropriate.
- 2) Coronary CTA for coronary plaque assessment. (This will not be performed if the subject has a previous reaction or contraindication to iodine-containing contrast media).
- 3) CT Abdomen for single slice screening at L4 for VAT determination.

Optional Blood Sampling Visit (For those who do not qualify after both screening visits): Subjects will present after an overnight 12 hr fast.

- 1) Fasting blood for markers of heart disease and inflammation

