Aim VI: In an exploratory analysis, subjects will be enrolled using a factorial sampling strategy into 4 analytic strata (low VAT/absence of plaque, low VAT/presence of plaque, high VAT/absence of plaque, high VAT/presence of plaque). Using this design, we will first analyze whether there are differences in markers of inflammation and heart disease by VAT status (main effects model comparing presence and absence of excess VAT) using student's t-test for variables that are normally distributed or Wilcoxon rank sum test for variables that are not normally distributed. Based on the exclusion criteria excess VAT is determined to be $>110\text{cm}^2$. After assessing for differences in VAT in the main effects model, we will examine the degree to which markers of inflammation and heart disease are related to coronary plaque in both the high and low VAT groups, and whether this relationship is stronger in the coronary plaque group as a result of increased VAT using ANOVA for variable that are normally distributed and Kruskal-Wallis Test for variables that are not normally distributed.

VII. Risks and Discomforts

Blood Drawing: The total blood drawn for subjects completing the study is equivalent to approximately 560 ml (over a period of 12 months). This quantity of blood drawing does not pose excessive risk to subjects. By comparison, the Red Cross allows a healthy adult to donate 1 pint of blood every 8 weeks, which is about 473 ml. Subjects with a hemoglobin < 10 mg/dL will be excluded from the study. There will be minimal risk and

Mineralocorticoid Receptor Antagonism for Cardiovascular Health in HIV The MIRACLE HIV Study

discomfort associated with blood drawing and IV placement. The risks of these procedures are minor bruising or bleeding at the site of the blood draw or IV catheter or feeling faint. Standard clean insertion techniques will be utilized to minimize risk of infection.

Intravenous Catheter Placement: There are minor risks and discomforts associated with having an intravenous line and with injection of contrast agent through the intravenous line, including the possibility of bleeding, pain, inflammation (redness and swelling), and leaking of contrast agent outside of the vein at the site of the IV. These problems usually self-resolve or only require minor treatments, such as application of an ice-pack or slight pressure for a few minutes.

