Written informed consent for this protocol will be obtained from all subjects at the first screening visit, prior to any procedures or interventions. In all cases, consent will be witnessed by an appropriate health care professional (investigator/co-investigator staff). All efforts will be made to insure the privacy rights of the subject. No written or oral communication will be made about any subject with anyone other than the subject, unless the subject so requests. Medical information obtained from the study may become part of the subject's permanent hospital record, subject to the confidentiality and privacy regulations of the Massachusetts General Hospital. Subjects will be closely monitored to ensure that study participation is not adversely affecting their quality of life, and any adverse events will be reported in a timely fashion and in accordance with the Partners HRC guidelines for adverse event reporting. PHRC requires the reporting of unanticipated problems, including risks, within 5 working days or 7 calendar days. Kidney function and potassium levels will be serially monitored. If a subject experiences an opportunistic infection or any acute illness, the lifestyle modification program will be held while the subject is acutely ill.

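### Hgb < 10 and ALT > 3.0x ULN are on-study exclusion limits, but no blood count or ALT is scheduled after Screening Visit 1

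*Combined protocol and SAP*

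**What the plan says.** Section IX lists the events that end participation after enrolment: "Exclusion criteria during the study include initiation of ACE-I, ARB, or spironolactone; Hgb < 10; ALT > 3.0x ULN; persistent hyperkalemia". The same paragraph adds persistent or symptomatic low blood pressure after a dose reduction.

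Section III sets the entry limits at the same values: "Hemoglobin < 10 g/dL" and "Known liver disease or ALT >3x ULN".

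In section V, the blood listed at Screening Visit 1 is: "Blood for Cr, K, ALT, CBC, HbA1c, and HIV viral load". At the six safety visits it is: "Blood for Cr, K. Blood for markers of heart disease and inflammation for the 6 month visit only". The remaining post-randomisation draws are at the Bionutrition Visit before month 12 and at the 12 Month Visit, which repeats Baseline Visit 1. Neither lists ALT or a blood count.

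On laboratory surveillance, section IX says: "Kidney function and potassium levels will be serially monitored". It makes no similar statement for haemoglobin or liver enzymes.

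**The concern.** A limit for staying in the trial works only if something measures the quantity it refers to. The other on-study criteria have a scheduled source at every safety visit: interval history for a newly started ACE inhibitor, ARB or spironolactone, blood for potassium, and vital signs for blood pressure. Haemoglobin and ALT have none.

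Because the entry and on-study limits coincide, a subject may be randomised with no margin on either test and then not be scheduled for it again. Someone who crosses a limit without symptoms would continue on study drug against the protocol's own rule. Whether the rule is applied would depend on whether a test happened to be done for another reason. The data safety monitoring board, which meets quarterly, would receive no scheduled haemoglobin or ALT results.

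**Working it through.** The plan states no figure on this point, so the check is a count of scheduled draws and the tests listed at each.

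**Post-randomisation draws in the main study (section V)**

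| Draw | Tests listed | ALT | CBC/Hgb | K |
|---|---|---|---|---|
| 1 week | Cr, K | no | no | yes |
| 2 weeks | Cr, K | no | no | yes |
| 4 weeks | Cr, K | no | no | yes |
| 3 months | Cr, K | no | no | yes |
| 6 months | Cr, K, heart disease and inflammation markers | no | no | yes |
| 9 months | Cr, K | no | no | yes |
| Bionutrition Visit before month 12 | Cr, K, lipids, glucose, insulin, CD4/8, viral load, biomarkers | no | no | yes |
| 12 Month Visit | PRA, aldosterone, K (serum pregnancy test for females) | no | no | yes |

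Number of draws: 6 safety visits + 1 Bionutrition Visit + 1 12 Month Visit = 8. ALT 0 of 8; CBC or haemoglobin 0 of 8; K 8 of 8; Cr 7 of 8.

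**Does another way of counting change the zero?** No.
- Baseline Visit 2, if counted as post-randomisation, lists PRA, aldosterone and K.
- Optional Substudy Visit 2 adds only a serum pregnancy test for females.
- The COVID-19 contingency plan allows local laboratories but adds no tests.

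**Length of the gap.** Dosing starts the day after Baseline Visit 2 and runs for 12 months with no scheduled ALT or CBC. The single test is older than that, because Screening Visit 2, the first Bionutrition Visit, Baseline Visit 1 and the 6-day low-sodium diet all fall between it and the first dose. With tests at 3, 6 and 9 months:
- longest nominal interval during dosing = 3 months;
- dosing left when each result arrives = 12 − 3 = 9, 12 − 6 = 6 and 12 − 9 = 3 months.

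The final interval could exceed 3 months where the contingency plan extends the schedule.

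**Extra blood.** Assumed CBC tube: 3–5 mL. Over three visits, 3 × 3 = 9 mL to 3 × 5 = 15 mL. Against the 560 mL stated in section VII (Blood Drawing), 9/560 = 1.6% and 15/560 = 2.7%, for a total of about 569–575 mL.

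**Number affected.** This cannot be estimated, since the documents give no rate at which subjects cross either limit.

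**The case against.** The strongest reply is that the hazards the protocol attributes to eplerenone are high potassium and low blood pressure, and both are closely monitored. The side effects listed in sections VII and IX include neither anaemia nor liver injury. Every safety visit also has an interval history and physical, and section IX says dizziness, fatigue and lack of energy are looked for throughout, so an investigator could order a test when symptoms suggest one. This stands. It limits the point to subjects without symptoms and to what the schedule itself can detect.

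A second reply is that section IX does not say how often either limit must be checked. One sentence saying that the limits apply to any result that becomes known would remove the mismatch. That is true, but it would detect no silent case.

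A laboratory might also run a blood count alongside CD4/8. The documents do not say so. The only such draw after randomisation comes at the end of treatment, and it would not supply ALT.

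Three stronger readings are tempting but unsupported:
- *That subjects are likely to be harmed.* No part of the protocol ties the drug to either abnormality, and no event rate is given.
- *That study blood-letting makes anaemia likely.* Section VII does put a haemoglobin limit in its blood-drawing paragraph, "Subjects with a hemoglobin < 10 mg/dL will be excluded from the study", but that sentence reads naturally as the entry criterion. The stated 560 mL over 12 months is also well below the donation pace the paragraph uses for comparison, 473 mL every 8 weeks.
- *That a breach can surface only through outside care.* Symptom-prompted testing at a visit is another route.

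**Conclusion.** The point holds as a gap between a stated rule and the visit schedule. Two on-study exclusion limits have no scheduled test after Screening Visit 1: 0 of 8 post-randomisation draws for each, against 8 of 8 for potassium. As written, the schedule cannot detect a subject without symptoms who crosses either limit during 12 months of dosing.

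The conclusion rests only on the tests listed in section V and the monitoring statement in section IX; no effect size or event rate is assumed. It is worth correcting because the sponsor set these limits and checking them costs little. It is not evidence of expected harm, and it changes no planned power, alpha or sample-size figure.

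**What to change.** Add ALT and CBC to existing safety-visit draws during dosing, and name both in section IX beside kidney function and potassium. Testing at 3, 6 and 9 months is one reasonable choice. The documents do not dictate the timing, and fewer tests would still be better than none.

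The cost is a protocol amendment, routine assays and the 9–15 mL of blood worked out above, with no extra visit. The volume assumes that ALT can be run on the chemistry sample already drawn for Cr and K, which the laboratory should confirm.

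A few subjects might be found over a limit and removed. The sample size allows 80 × 0.15 = 12 losses, leaving 68 evaluable. Not every removal need use one of those places: section VI (Statistical Consideration, Aim I) provides for end-of-study biomarkers and imaging in subjects who withdraw after 6 months and agree to it, so later removals may remain evaluable.
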